### **Recruitment and Screening Strategies for Clamp Studies**

Recruitment of middle aged subjects will be predominantly by local advertising. This will include posting flyers within Einstein and around the neighborhood and posting advertisements in area newspapers. [name]" research group has had considerable success with these approaches in the recruitment of many middle aged, nondiabetic subjects to date.

**Screening:** This visit will include a full history and physical examination, an oral glucose tolerance test and additional laboratory tests to determine eligibility, including serum electrolytes, BUN and creatinine, PT/PTT, liver function tests, CPK, and lipid profile, as well as a screening urinalysis, urine toxicology screening, and blood pressure measurements. Safety laboratories will be repeated during the first and second pancreatic clamp studies and include: CBC, chemistry, liver function tests, CPK, and urinalysis.

All subjects will present to the CRC fasting; consequently, visits will be scheduled in the morning. The oral glucose tolerance tests (only non-diabetic subjects) will consist of a 75g oral glucose challenge in the form of a beverage, with fasting (immediately prior to drinking beverage) and 2 hour venous blood samples for plasma glucose and insulin measurements. Physical examination will include a careful assessment of upper extremity veins, as well as measurement of height and waist circumference and percent body fat (by body impedance absorptiometry). Since public transportation in our local area is limited and many area residents do not drive, we will make arrangements to provide transportation to and from clinic visits, including screening visits, for all participants who require it.

### **General Experimental Conditions:**

On the day of the first pancreatic clamp study the patients will receive a 28 days" supply of resveratrol capsules. The pilot study will be an open-labeled study. The study design requires that all 55 subjects participate in all of the proposed studies, as outlined below. Consequently, additional subjects will be recruited to compensate for those subjects who cannot complete all of the required studies.

Prior to each study, subjects will meet with study personnel to discuss dietary recommendations. Each subject will be instructed to follow a standardized diet plan for three days prior to each of the clamp studies (40% fat: 20% saturated, 10% polyunsaturated, 10% monounsaturated; 35% carbohydrate; 25% protein). Subjects will be asked to refrain from vigorous exercise for three days prior to each clamp study.

### **Aim 1: To study the effects of resveratrol on age-related insulin resistance**

*We hypothesize that treatment of overweight, middle aged or Type 2 diabetes subjects with resveratrol will result in improved insulin sensitivity, as demonstrated by increased insulin-stimulated glucose uptake and enhanced insulin-mediated suppression of glucose production.*

We will study the following subject group:

- **Overweight and either young or middle aged** (BMI 25-30 kg/m^2, age 21-65) nondiabetic subjects, n=40 diabetic subjects (BMI=25-35) n=15

Each subject will receive a 28 day course of **resveratrol** (n=55). RevGenetics will supply the resveratrol (500 mg capsules; 2 capsules bid) for our proposed studies. A certificate of analysis has been provided by the manufacturer.

A comprehensive study of whole-body insulin action will be undertaken with specially designed „stepped” euglycemic (~90 mg/dl) -hyperinsulinemic clamp studies, both before and after administration of resveratrol.

Thus, we will compare the following parameters under paired conditions in each subject, on day 0 and day 28 of resveratrol treatment:

- a. **hepatic insulin action:** this will be determined as the ability of low infusion rates of insulin (20 mU/m^2.min above basal requirements) to suppress glucose production during the “**low insulin phase**” of the clamp studies.
- b. **peripheral insulin action:** this will be determined as the ability of high infusion rates of insulin (80 mU/m^2.min above basal requirements) to stimulate glucose uptake during the “**high insulin phase**” of the clamp studies.

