7. Resveratrol: Resveratrol is present in significant amounts in a variety of foods, including grapes, blueberries, peanuts and red wine and over-the-counter resveratrol supplements are widely used. Formal safety testing is not required for marketing of nutritional supplements, but to date, there have been no published reports of side effects at the commonly used doses (up to 1000 mg /day). A number of *in vitro* studies have demonstrated that resveratrol can be an inhibitor of various cytochrome P450 enzymes that are involved in drug metabolism. The relevance of these *in vitro* observations to *in vivo* use is unclear primarily because oral resveratrol is rapidly metabolized by the liver, free resveratrol levels are quite low and resveratrol metabolites have not been shown to be inducers or inhibitors of CYP enzyme activity. Nonetheless, caution is warranted, especially for drugs with a narrow therapeutic window (anti-epileptics, mexilitene, quinidine, cyclosporine, tacrolimus, HIV protease inhibitors) and use of these drugs will be exclusionary for this study. Furthermore, due to the potential estrogenic effects of resveratrol, a medical history of ovarian, uterine, and breast cancer will be exclusionary for the study.
8. Somatostatin: At the proposed physiological replacement doses has no known side effects.
9. Ocreotide: At the proposed physiological replacement doses has no known side effects.

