**2. ADEQUACY OF PROTECTION AGAINST RISKS****Recruitment and Informed Consent Procedures:**

We will recruit at least 40 overweight, middle aged, nondiabetic subjects and 45 subjects with Type 2 diabetes by local advertising. Consent will be initially obtained during telephone screening performed by a research fellow or the study coordinator. Formal consent procedures which adhere to the Committee on Clinical Investigations of the Albert Einstein College of Medicine will be followed. Specifically, each subject will be verbally informed in layman's language of the purpose, benefits and possible risks of the studies. They will then read the written consent form in the presence of a member of the research team and a physician who will answer any further questions. The subject and

witness shall be asked to sign the consent form which will be kept in the patient's chart. Each subject's potential participation in related experiments (for example, when each subject is asked to perform repeat studies) will be explicitly stated.

All clinical data on the subjects will be confidential. Data generated in these studies will be considered only relevant for research purposes and will not be included in any clinical databases or the patient's chart. Since the GCRC databases are coded, the study data will not be available on any clinical database system.

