### **Protection Against Risk:**

#### **Procedures employed to protect subjects from undue risks include the following:**

- 1) Blood withdrawal: Blood withdrawal during any single study will be limited to less than 190cc and subsequent studies will be separated by at least, a four week interval. The infusion and withdrawal catheters may produce infection or local hematoma, but strict aseptic technique will be observed by the experienced physician performing the procedure.
- 2) 20% glucose: Vein irritation with 20% glucose infusion will be prevented by use of a large-bore antecubital vein.
- 3) Glucagon: Symptoms of mild nausea will be treated with antiemetic medications, if needed.
- 4) Hypoglycemia: All of these studies will be performed by a physician, hypoglycemia will be prevented by blood glucose sampling every 5-10 minutes and if inadvertent hypoglycemia develops can be rapidly treated by glucose infusion.
- 5) Resveratrol: Given data from a number of *in vitro* studies demonstrating that resveratrol can be an inhibitor of various cytochrome P450 enzymes involved in drug metabolism, use of the following drugs will be exclusionary for this study: anti-epileptics, mexilitene, quinidine, cyclorpsorine, tacrolimus, HIV protease inhibitors. Dosages of up to 1000 mg/day have been widely used without reports of adverse effects.

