**Adverse Event Monitoring:**

Process: Data and safety monitoring for this study will be performed by the principal investigator on an ongoing basis. All volunteers will be seen by the P.I. or her research staff. Laboratory data will be reviewed by the P.I. within 24 hours of receipt.

Reporting: All adverse events will be compiled, and reported in summary form, on an annual basis to the IRB, and at the conclusion of the study. Unanticipated (non-serious) adverse events will be reported to the IRB within 30 days and serious adverse events will be reported to the IRB within 48 hours by phone, email or fax

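### The assigned resveratrol regimen works out to 2000 mg/day, but the protocol's dose-specific safety statements stop at 1000 mg/day and nothing acknowledges the gap

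*Combined protocol and SAP*

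**What the plan says.** The regimen appears once, in the Aim 1 section under Experimental Approach and Methods: "500 mg capsules; 2 capsules bid". The same paragraph applies it to everyone: "Each subject will receive a 28 day course of resveratrol (n=55"). General Experimental Conditions confirms the reach: "The study design requires that all 55 subjects participate in all of the proposed studies".

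A resveratrol dose in mg appears in only two other places:

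- Potential Risks, item 7: "there have been no published reports of side effects at the commonly used doses (up to 1000 mg /day").
- Protection Against Risk, item 5, within the list of procedures that protect subjects: "Dosages of up to 1000 mg/day have been widely used without reports of adverse effects".

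The Rationale section also asserts that long-term administration is safe, but it names no dose.

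Some protections do not depend on dose. There are exclusions for interacting drugs and for certain cancer histories. Laboratory checks are planned: "Safety laboratories will be repeated during the first and second pancreatic clamp studies". Oversight is assigned: "Data and safety monitoring for this study will be performed by the principal investigator on an ongoing basis". The Early Study Termination section provides for stopping after an unanticipated, related serious event.

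**The concern.** Multiplied out, the Aim 1 regimen is twice the highest dose mentioned in either risk section. A reader who sees only the risk sections would conclude that the study dose lies within the range of reported use. A reader who multiplies out the regimen would see that it does not. No sentence in the available text connects the two.

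What is at stake is whether the risk description matches the treatment. Protection Against Risk offers the 1000 mg/day experience as one of the safeguards, and that experience does not extend to the dose assigned. Potential Risks itself notes that supplements can be marketed without formal safety testing, so reported use is the only dose-specific human safety support the protocol offers. The ethics committee weighs risk on the strength of these sections. The protocol also promises to tell each subject the "purpose, benefits and possible risks of the studies". The consent pages are not in the text available, so what subjects are actually told is unknown.

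**Working it through.** No sample size or power figure is involved; the check is a multiplication set against a stated range. The protocol prints no daily total, so there is no printed sum to reproduce.

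**Inputs**

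| Quantity | Value | Source |
|---|---|---|
| Capsule strength | 500 mg | Aim 1 |
| Capsules per intake | 2 | Aim 1 |
| Intakes per day (bid) | 2 | Aim 1 |
| Duration | 28 days | Aim 1 |
| Subjects | 40 + 15 = 55 | Aim 1; Human Subject Characteristics |
| Top of cited experience | 1000 mg/day | Potential Risks, item 7; Protection Against Risk, item 5 |

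**Assigned dose**

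- Per intake: 500 mg × 2 capsules = 1000 mg.
- Per day: 1000 mg × 2 intakes = 2000 mg, or 4 capsules.
- Per course: 2000 mg × 28 days = 56,000 mg, or 4 × 28 = 112 capsules.

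**Against the cited experience**

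- Ratio: 2000 / 1000 = 2.0.
- Difference: 2000 − 1000 = 1000 mg/day.
- One of the two daily intakes already reaches the top of the cited range.

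**Alternative reading.** If the notation meant two capsules in total per day, one at each intake, the dose would be 500 mg × 2 = 1000 mg/day and would match the risk sections. That is not the ordinary meaning of the notation, and no section supports it. If it were intended, Aim 1 would still need rewording, because as written it would be dispensed at twice that amount.

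**Other text that might close the gap.** The Rationale section's safety remark carries no dose. The remarks in Potential Risks on rapid metabolism and low free levels are made about cytochrome P450 interactions, not about tolerability at any particular dose. For the glucose tracer, glucagon, growth hormone, somatostatin and octreotide, the risk text refers to the doses this study will use. For resveratrol, the agent under test, it refers to doses in general use.

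**Monitoring.** The laboratory checks fall at the two clamps. By the Schedule of proposed clinical studies these are on day 0, before dosing on days 1–28, and on day 28, the day of the last dose. The first set is therefore a baseline, and the only scheduled set after dosing begins comes at its end.

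**The case against.** The strongest reply is that nothing here is contradictory in the strict sense. Aim 1 states what this study gives; the risk sections describe what people commonly take. All of these can be true together, and 1000 mg/day is nowhere set as a ceiling. That is correct as far as it goes. What remains is a gap in safety support: background experience is offered as protection for a regimen it does not cover, and the text does not say so.

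Second, a dose rationale may sit in pages that were not available, in particular the consent form. That also stands, and it is why no conclusion is drawn about what subjects are told. It does not repair the risk sections, which should match the regimen in their own protocol.

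Third, the drug and history exclusions, the safety monitoring and the termination rule protect subjects whatever the dose. They do, and they count in the plan's favour. The exclusions, however, address drug interactions, bleeding and estrogenic effects, and none of these provisions supplies experience at the assigned dose.

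Fourth, the figure of 55 can be questioned. Recruitment Monitoring and Table II give 40, the Recruitment and Informed Consent Procedures section gives 45 subjects with diabetes, and Statistical Analysis still describes a placebo group. The sections that describe treatment agree on 55, and no section gives resveratrol at another dose. Because non-completers are to be replaced, the number dosed could be higher.

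Finally, one may say that a matter of wording is not critical, since inference is unaffected. The grounds for requiring the change are the accuracy of the risk section for the sole study treatment, not statistical validity.

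**Conclusion.** The concern holds. The written regimen is 2000 mg/day, 2.0 times the 1000 mg/day at which both dose-specific safety statements stop. It applies to all 55 subjects under the treatment sections. The available text neither acknowledges the difference nor supports the higher figure.

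This rests on the ordinary reading of bid and on the text available, which excludes the consent pages. It is a mismatch between the regimen and its cited safety support. It is not evidence that the dose is unsafe, and no view is taken on which figure is right. Because it bears on the safety case for the study drug in every subject, it should be resolved before anyone is dosed under this text.

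**What to change.** Reconcile Aim 1, Potential Risks (item 7) and Protection Against Risk (item 5):

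1. In Aim 1, state the total daily dose in mg beside the capsule instructions, so that only one reading is possible.
2. In both risk sections, either give the safety basis for the dose actually assigned, or say plainly that the cited experience stops at half of it.
3. Check that the consent form agrees with the reconciled text, and revise it only if it does not.

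The dose itself is a decision for the responsible clinicians.

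The cost is protocol wording and notification of the ethics committee, plus consent wording if the form disagrees. The risk statement may read less favourably afterwards. The endpoint, sample size and analysis are unaffected.

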### In vivo clamp studies – General Conditions

Subjects will be admitted on the day of the study to the General Clinical Research Center (GCRC) study room after an overnight fast. Subjects with type 2 diabetes will be admitted to the Jack Weiler Hospital of the Albert Einstein College of Medicine the night before the study. All anti-diabetic medications, including insulin, will be held from one day to one week prior to the clamp study date depending on the drug they are taking. They will not eat after 10 PM the night before the study (but can drink water). An intravenous catheter will be inserted into their left arm and insulin will be administered overnight to maintain their glucose at normal levels. Blood samples will be collected every hour for glucose values. At 8:00 am 2 intravenous cannulae will be established, one for infusions and a second one to be inserted in a retrograde fashion in a dorsal vein of the opposite arm for blood sampling. To obtain arterialized venous blood samples, this hand will be maintained at 65°C in a thermoregulated plexiglass box.

[figure not shown]
A primed continuous infusion of D2G-glucose will be initiated at t=-120 min (2 hours prior to the onset of the „clamp” study). A bolus of 200 mg/m^2 D2G for the duration of 3 min will be followed by a continuous infusion of 2 mg/min/m^2 D2G for the entire study in all subjects (for total duration of 6 hours) to **quantify glucose turnover**, specifically rates of peripheral glucose disposal and hepatic glucose production.

These „pancreatic clamp” experiments will consist of 360 min insulin/somatostatin (250 µg/hr) or insulin/octreotide (30 mg/kg/min) infusions with replacement of glucoregulatory hormones (glucagon 1 ng/kgmin; growth hormone 3 ng/kgmin). Throughout the entire 360 min the plasma glucose concentration will be maintained at basal levels (~90 mg/dl).

**Basal phase:** From t=0 min to t=120, optimal insulin infusion rates will be selected in each individual by making frequent (~ every 25 mins) adjustments to the insulin infusion rates in order to establish those insulin infusion rates required to maintain euglycemia (90 mg/dl) without the requirement for exogenous glucose infusion.

**Low phase:** Following establishment of basal insulin requirements during the basal phase, at t=120 the insulin infusion rate will be increased by a fixed increment of 20 mU/m^2/min, and will be maintained at this rate for 2 hours (T=120-240). Plasma glucose will be maintained at euglycemic concentrations (~90mg/dl) by a variable infusion of 20% dextrose for the entire study (78).

**High phase:** At t=240 min, insulin infusion rate will be increased to 80 mU/m^2/min above basal requirements, and will be maintained at that rate for the final 2 hours of the study (t=240-360).

**Plasma measurements:** From t=0 to t=360 min., blood samples will be obtained at hourly intervals for determinations of plasma glucose, insulin, glucagon, C-peptide, growth hormone, free fatty acids (FFA), glycerol, and lactate. Additional samples for D2G determinations will also be obtained every 15 min. Plasma glucose will be measured every 5-10 min in duplicate by a Beckman glucose analyzer. Plasma lipids (LDL, HDL, VLDL, total Cholesterol and Triglycerides) will be measured

at t=0.

**Biopsies:** From t=225-240 min, fat and muscle biopsies will be obtained. Participants will have fat biopsies performed in the periumbilical region. A small 0.5 cm cutaneous incision will be performed under local anaesthesia (Lidocaine 1% with Epinephrine) and 1-2 g of adipose tissue will be obtained by aspiration technique (79). A skeletal muscle biopsy will be obtained from vastus lateralis muscle using a cadence muscle biopsy needle following local anaesthesia extending into the muscle area. The total amount of muscle obtained will be ~300 mg. The biopsy specimens will be immediately homogenized in Trizol at the bedside, to inhibit any RNAase activity, and will subsequently be stored at -80 °C. Pressure will be applied at the biopsy site for ~10 min following the biopsy. A pressure bandage will be applied and kept on 5-6 hours after the biopsy. Since the biopsies are performed in 4 hours into the clamp and the subject will undergo direct observation for an additional 3-4 hours. The biopsy site will be examined prior to discharge and a pressure bandage will be reapplied for an additional two hours. Subjects will be able to remove the bandage once they get home.

All infusions will be stopped at t=360 min. The patient will be given a standard meal and plasma glucose levels will be monitored at 15-30 min intervals for the next one hour. Dextrose infusion will be continued for approximately 45 minutes after the study in order to avoid hypoglycemia. The patient will be discharged after about one hour, provided that his or her condition remains stable.

**Indirect Calorimetry.** A PARVO MEDICS, (TrueOne® 2400 Metabolic Measurements Systems) will be used to estimate rates of carbohydrate and lipid oxidation from T=260-280 in all studies. Twenty minute averaged values for VO2 and VCO2 will be corrected for nitrogen excretion as urinary urea nitrogen measured enzymatically by the method of Kjeldahl (80). Net glucose and lipid oxidation rates will be calculated from indirect calorimetry. The equations used to calculate glucose and lipid oxidation from gas exchange and urinary urea nitrogen excretion have been published (81). Under conditions in which RQ > 1.0, the overestimation of glucose oxidation will be corrected as described (81).

**Analytical procedures –** Plasma glucose will be measured with a Beckman glucose analyzer (Fullerton, CA) by use of the glucose oxidase method. Measurements of plasma insulin, C-peptide, glucagon, and growth hormone are undertaken throughout the studies in order to evaluate the adequacy of the “pancreatic clamp” technique, ie. inhibitory effects of somatostatin on hormone secretion, and uniformity of hormone replacement. All samples will be kept on ice until centrifuged (within 30 min). Plasma samples will then be sorted and handled by the Special Assay Core, and will be stored frozen at -20°C for later assays. Plasma hormone determinations will be performed by radioimmunoassay as previously reported (82), and these determinations will be provided by the Radioimmunoassay Core of the Diabetes Research and Training Center.

**Substrate determination-** Plasma FFA levels will be determined by using an acyl-CoA oxidase based colorimetric kit (Wako, Osaka, Japan) and glycerol will be measured using colorimetric enzymatic methods (83,84). Plasma lactate will be measured by fluorometric enzyme techniques (85).

**Glucose Kinetics-** Plasma for labeled glucose radioactivity will be treated as previously described (86). Rates of glucose appearance (Ra) and disappearance (Rd) and other indices of glucose turnover will be estimated by using the steady-state equation of Steele (87). Endogenous glucose production (EGP) will be determined by subtracting the rates of glucose infusion from the tracer-derived rate of appearance of glucose. Data for glucose turnover represent the mean values during the final 60 min of the low insulin period (t=60-120 min), and during the final 60 min of the hyperglycemic period (t=180-240 min).

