### STATISTICAL ANALYSIS

Data collected from each subject will be edited, entered, verified and entered into a FoxPro data base system in the GCRC. Data quality checking will be performed by computer programs designed to detect errors using accepted ranges, logic checks, and missing values. Outliers will be checked against the original record and correct values will be entered into a final data file. Data from FoxPro files will be transferred into SAS System Version 6.12 (SAS Institute, Cary, NC) for analysis. We shall utilize SAS for all data management and statistical analysis. Descriptive statistics of all the variables at different time points will be derived and reported.

For the specific aims of this study, repeated measurements of several parameters including glucose metabolism and gene expression will be measured in each subject, with the principal endpoint being the rate of whole-body glucose uptake during the final hour of the high insulin clamp. The null hypothesis is that glucose uptake will be equal in each pair of experiments (ie. prior to and following 45 days" treatment with resveratrol or placebo). To determine the changes in glucose uptake between the paired experimental protocols for each subject group, paired Student's t-tests will be performed. For *between-group* comparisons (ie. between the two subject groups randomized to resveratrol or placebo), the principal endpoint will be the difference in whole-body glucose uptake ( $\Delta$ GU) between the 2 experimental conditions (eg. Resveratrol vs. placebo), with null hypothesis that the response to the experimental intervention will be the same in all subject groups. To determine the changes in glucose uptake between the paired experimental protocols for each subject group, analysis of

variance (ANOVA) will be performed by using PROC GLM in the SAS statistical package. Within group effects will be derived from the analysis.

*All values will be presented as the mean +/- SE.*

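### The stated 6-hour D2G tracer duration contradicts the tracer's own start and stop times (8 hours), and the glucose-turnover windows miss the principal endpoint hour

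*Combined protocol and SAP*

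**What the plan says.** All tracer and clamp times are under In vivo clamp studies – General Conditions in the combined protocol and SAP.

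- **Tracer start.** "A primed continuous infusion of D2G-glucose will be initiated at t=-120 min", two hours before the clamp.
- **Tracer extent.** A 3-minute bolus is followed by a constant 2 mg/min/m² infusion of "D2G for the entire study in all subjects (for total duration of 6 hours".
- **Clamp length.** "Throughout the entire 360 min the plasma glucose concentration will be maintained at basal levels".
- **Phases.** Basal: "From t=0 min to t=120, optimal insulin infusion rates will be selected in each individual". Low insulin: t=120-240. High insulin: the rate "will be maintained at that rate for the final 2 hours of the study (t=240-360".
- **D2G sampling.** Every 15 min, listed straight after a sentence that sets the plasma sampling period as t=0 to t=360.
- **Stop.** The closing paragraph of the clamp description stops all infusions at t=360. It then keeps dextrose running for about 45 min afterwards, which does not bear on the tracer.

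The Glucose Kinetics paragraph obtains Ra and Rd from the steady-state Steele equation, and endogenous glucose production (EGP) as tracer-derived Ra minus the glucose infusion rate. It averages turnover over t=60-120, labelled low insulin, and t=180-240, labelled hyperglycemic.

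Statistical Analysis names "the principal endpoint being the rate of whole-body glucose uptake during the final hour of the high insulin clamp".

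**The concern.** One sentence gives the tracer two extents that cannot both hold with the stated start. Someone preparing syringes or writing an order from the 6-hour figure, counting from t=-120, would stop the tracer as the high-insulin phase begins.

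That phase contains the principal endpoint. The steady-state equation needs a constant tracer infusion that is still running. Without one, Rd and EGP cannot be computed as planned, and the lost measurement cannot be recovered later. The only measure left for that hour would be the dextrose infusion rate (GIR), which omits any glucose the liver is still producing. At steady state GIR = Rd − EGP, so the paired change would be ΔGIR = ΔRd − ΔEGP. Aim 1 hypothesises an effect on glucose production as well as on uptake, so a GIR-based contrast could mix the two.

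**Working it through.** **Inputs.** Tracer start t=-120; stated duration 6 h = 360 min; clamp t=0-360; high phase t=240-360; infusions stopped at t=360; endpoint hour = last 60 min of the high phase = t=300-360.

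**Step 1: try to reproduce the 6 hours.** Stop − start = 360 − (−120) = 480 min = 8 h. The stated figure is not reproduced; it is 120 min shorter.

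**Step 2: follow the 6 hours from the stated start.** −120 + 360 = t=240. If the six hours are counted from the end of the 3-minute bolus, the end is t=243, which still falls 57 min before the endpoint hour.

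**Step 3: minutes with running tracer under each reading.**

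| Window | 6 h from t=-120 (ends t=240) | Stop at t=360 (8 h) |
|---|---|---|
| Basal, t=0-120 | 120 of 120 | 120 of 120 |
| Low, t=120-240 | 120 of 120 | 120 of 120 |
| High, t=240-360 | 0 of 120 | 120 of 120 |
| Endpoint hour, t=300-360 | 0 of 60 | 60 of 60 |

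Under the short reading, the endpoint hour starts 300 − 240 = 60 min after the tracer stops and ends 360 − 240 = 120 min after.

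**Step 4: amount of tracer.** Ignoring the bolus, 2 × 360 = 720 mg/m² against 2 × 480 = 960 mg/m². The difference is 240/960 = 25%.

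**Step 5: which timelines do give 6 hours?**

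- Clamp only, t=0-360: 360 min. This leaves the two-hour lead-in out of a figure described as a total.
- t=-120 to t=240, that is, a 240-min clamp: 240 − (−120) = 360 min. This contradicts the 360-min clamp and the stated high phase.

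**Step 6: the turnover windows against the phases.**

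| Glucose Kinetics window | Label there | Phase in the clamp section |
|---|---|---|
| t=60-120 | low insulin | second hour of the basal phase |
| t=180-240 | hyperglycemic | final hour of the low-insulin phase, at about 90 mg/dl |
| none | – | t=300-360, the principal endpoint hour |

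Both windows fit a clamp ending at t=240, as does a 6-hour tracer begun at t=-120.

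**The case against.** A reader might infer that, as written, the tracer ends at t=240 and the principal endpoint has no tracer. The documents do not support that. The sentence with the 6-hour figure also says "D2G for the entire study in all subjects", the section stops all infusions at t=360, and the D2G sampling plan follows a t=0 to t=360 sampling period. No section gives t=240 as a tracer stop; it appears only when the parenthetical is added to the start time.

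There is also an innocent reading. The clamp itself lasts 360 min, and the parenthetical may loosely describe that. The t=-120 lead-in is stated separately and would stand, so no tracer would be lost. A figure just before this text is not available here and may show the timeline. Harm needs staff to follow the parenthetical over the other statements, and no preparation or order sheet is among the documents.

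All of this stands, and it makes the consequence conditional. It does not remove the contradiction, because the innocent reading still makes the word total wrong. Nor is the figure clearly an isolated slip, since the Glucose Kinetics windows also fit a study ending at t=240. That both come from an earlier design is possible, but the documents do not say so.

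A reader might also infer that falling back on the dextrose rate would bias the diabetic subjects most. The documents give no residual glucose production for either group in the high phase, so that cannot be claimed.

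**Conclusion.** The stated total of 6 hours is wrong against the stated start and stop, which give 8 hours: a discrepancy of 120 min, or 25% of the constant infusion. The other statements in the clamp section imply a tracer meant to run to t=360. Only if the 6-hour figure is followed from t=-120 is the endpoint hour left with no running tracer.

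The mismatch in the turnover windows does not depend on how the 6 hours is read. Neither window lies in the high-insulin phase, so the analysis text nowhere averages turnover over the hour that Statistical Analysis makes principal.

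Two assumptions are needed. The endpoint hour is t=300-360, taken from the high-phase times because Statistical Analysis gives no minutes. Whole-body glucose uptake is tracer-derived Rd, which follows from the stated purpose of the tracer and from Glucose Kinetics but is not spelled out in Statistical Analysis. No power, variance or dropout assumption enters.

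**What to change.** The investigator should reconcile five items into one timeline: the tracer start, stop and total duration under In vivo clamp studies – General Conditions, the averaging windows and their labels under Glucose Kinetics, and the endpoint hour in Statistical Analysis. Statistical Analysis should give the endpoint window in clamp minutes and say that uptake is tracer-derived Rd, if that is the intention. The same timeline should then go into infusion preparation, the D2G sampling schedule and the analysis program. Which infusion duration is right is for the investigator to state.

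If any clamps have been run, read the actual tracer stop times from the study records before analysing the endpoint.

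The cost is a few lines of protocol text and matching worksheets. More tracer is needed only if the reconciled duration is longer than what is now being prepared, which the documents do not show.
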